2.2 Rationale for Current Study

A previous Phase II study (Study CT-P27 2.1) demonstrated trends favoring the efficacy of low doses of CT-P27 on viral shedding measures and total symptom scores in healthy volunteers. The proposed Phase IIb study will evaluate the efficacy and safety of two doses of CT-P27 (45 mg/kg and 90 mg/kg) in subjects with acute, uncomplicated influenza A. This study was designed to obtain an effect size of CT-P27 in comparison to placebo based on time to resolution of influenza symptoms and fever (see [Section 8.1](#)). Information on effect size, as

well as the safety, efficacy, and PK of CT-P27 at 45 mg/kg and 90 mg/kg will be used in the selection of doses in subsequent studies.

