8.5 Statistical Analyses

8.5.1 Primary Efficacy Analysis

The primary efficacy endpoint analysis will assess the time (in days) from the administration of study drug to resolution of influenza symptoms and fever. This analysis will be performed on the ITTI population. Data will be obtained from responses recorded on the Flu-iiQ™.

Resolution of symptoms has occurred if the following influenza symptoms (as recorded on the Flu-iiQ™) are mild in intensity or none for at least 24 hours.

- Respiratory symptoms (cough, sore throat, and nasal congestion).
- Constitutional symptoms (headache, feeling feverish, body aches and pains, and fatigue).

Resolution of fever is defined as:

- Body temperature of $<37.0^{\circ}\text{C}$ for at least 24 hours. (The start time for resolution of fever is defined as the time recorded in the diary when body temperature was $<37.0^{\circ}\text{C}$ for at least 24 hours.)

If the subject has received the drugs for symptom relief, the effective duration of the drugs for symptom relief should be considered.

For example, the study drug was administered at 12:00 on 1st day. The first time body temperature recorded $<37.0^{\circ}\text{C}$ in the diary was 10:00 on 2nd day and continued more than 24 hours. But acetaminophen/paracetamol known to be effective for 6 hours had been administered at 09:00 on 2nd day [1 hour prior to the time when the body temperature decreased $<37.0^{\circ}\text{C}$], it will be calculated that the start time point for body temperature $<37.0^{\circ}\text{C}$ is 15:00 on 2nd day [27 hours after the study drug administration]. Then, if the next first time body temperature recorded $<37.0^{\circ}\text{C}$ in the diary was 22:00 on 2nd day and body temperature was $<37.0^{\circ}\text{C}$ for 24 hours from then, the start time for resolution of fever is 22:00 on 2nd day [34 hours after the study drug administration].

The primary efficacy endpoint will be analyzed using a Wilcoxon rank-sum test to assess differences between treatment groups, if every subject were followed until resolution of influenza symptoms and fever. The statistically significant difference of time to resolution of influenza symptoms and fever between placebo and CT-P27 based on Wilcoxon rank-sum test will be presented by p-values. If there is any censoring, the primary efficacy endpoint will be analyzed using Log-rank test, and Kaplan-Meier plots will be presented.

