These data will be used to determine the efficacy of treatment with CT-P27 to establish an effect size of CT-P27 in comparison to placebo based on time to resolution of influenza symptoms and fever. Information on effect size, as well as the safety and PK will be used in the selection of doses for subsequent clinical studies.

2. Objectives

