5.1 General Analysis Considerations

The statistical analysis will be performed using [REDACTED]. Any deviations from the planned analysis as described in this SAP will be justified and recorded in the CSR.

The data documented and the clinical parameters measured in this study will be described using descriptive statistics (including number [n], mean, median, Standard Deviation (SD), minimum, and maximum) for continuous variables: minimum and maximum will be presented to the same number of decimal places as the raw data, mean and median will be presented to one more decimal place than the raw data, and SD will be presented to two more decimal places than the raw data. If the geometric mean is to be presented, it will be set to the same precision as the mean. However, geometric mean will not be calculated when minimum value from the data is zero. Percent Coefficient of Variation (CV%) will be presented to two decimal places. P-values will be rounded to three decimal places. If a p-value is less than 0.001 it will be reported as "<0.001". If a p-value is greater than 0.999 it will be reported as ">0.999".

Categorical data will be summarized using count and percentage in each category. Percentages will be presented to one decimal place. The percentage will be suppressed when the count is zero in order to draw attention to the non-zero counts. "Not done" and "Missing" category will be included to account for cases of no assessment and missing respectively even if they are not recorded in eCRF. The denominator for all percentages will be the number of subjects within the treatment group for the population of interest, unless otherwise indicated.

All data will be displayed in listings. Unless otherwise specified, listings will be sorted by the treatment group, subject number, and assessment date or visit date, if applicable. In cases where more ordering is required, other variables will be included in the sort order as applicable.

Baseline will be the latest available measurement prior to the start of the infusion of study drug.

When summarizing End-of-Study (EOS) visit, the early termination cases are excluded from the summary for EOS visit, but will be presented in data listings. Unscheduled results will not be included in the summary tables except for determining baseline or if unscheduled results are necessary to interpret data, but they will be presented in data listings.

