5.2 Determination of Sample Size

This study is designed to obtain effect sizes of 2 different CT-P27 treatment groups and placebo group based on the time from the administration of study drug to resolution of influenza symptoms and fever.

For this proof-of-concept dose-ranging study, assuming 90% of subjects are included in the eligible infected population, the total eligible sample size of 164 (63 eligible infected subjects per CT-P27 treatment groups and 38 subjects in placebo group) achieves 80% power to detect 1.8 days of reduction for the primary endpoint of time to resolution with 5% two-sided significance level and SD of 3 days using a Wilcoxon's rank-sum test.

Considering a dropout rate of 10%, this study will need 183 subjects to be enrolled to achieve 164 evaluable subjects.

For an effect size of 1.5 days of reduction in time to resolution with SD of 2.9 days, the total sample size could be increased to about 250 to achieve at least 80% statistical power with 5% two-sided significance level.

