10.1 Primary Efficacy Analysis

The primary efficacy endpoint analysis will assess the time from the administration of study drug to resolution of influenza symptoms and fever. The Flu-iiQ™ and body temperature recorded in diary including records as

Statistical Analysis Plan

a part of suspicious ADE assessment will be used for the analysis. The Flu-iiQ™ is a validated questionnaire with four domains. This includes the Domain 1; intensity of influenza symptoms, Domain 2; impact on activities, Domain 3; effects on feelings and Domain 4; concerns due to influenza. Subjects are offered four choices, ranging from the most positive response (e.g., none or not at all) to the most negative choice (e.g., severe or great difficulty). This analysis will be performed on the ITTI population.

The definitions of resolution of influenza symptoms and fever are described below.

Resolution of symptoms has occurred if all of the following influenza symptoms (as recorded on the Flu-iiQ™ of Domain 1) are mild in intensity or none for at least 24 hours. (4-point scale - 0: None, 1: Mild, 2: Moderate, 3: Severe).

- Respiratory symptoms (cough, sore throat, and nasal congestion)
- Constitutional symptoms (headache, feeling feverish, body aches and pains, and fatigue)

Resolution of fever is defined as:

- Body temperature (as recorded in the diary) of $<37.0^{\circ}\text{C}$ for at least 24 hours.

The start time for resolution of influenza symptom and fever is defined as the start time when symptoms and fever are resolved, whichever occurred latest.

The time (in days) from the administration of study drug to resolution of influenza symptoms and fever will be calculated as follows: [Start date/time of resolution of influenza symptoms and fever] – [Start date/time of study drug administration]. If time of completion of diary for Flu-iiQ™ and body temperature is missing then the time will be assumed to be 10:00 AM and 10:00 PM for Morning and Evening, respectively.

If the subject has received the drugs for symptom relief, the effective duration of the drugs for symptom relief should be considered in determining the start time for resolution of symptom and fever.

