The primary efficacy endpoint will be analyzed using a Wilcoxon rank-sum test to assess differences between treatment groups (CT-P27 45 mg/kg vs placebo, CT-P27 90 mg/kg vs placebo), if every subject is followed until resolution of influenza symptoms and fever. The Wilcoxon rank-sum test will be used to test for a statistical significant difference of time to resolution between placebo and CT-P27. The results of the analysis will be summarized using p-values. The significant level will be set to 5%. If p-value is lower than 5%, it is considered that there is a significant difference between placebo and CT-P27. For subjects who withdrew from the study before the symptoms have resolved or if the symptoms did not resolve until the data cut-off, data will be censored at the latest date/time recorded on the diary or start date/time of study drug administration when there are no recorded data on the diary after study drug administration. If there is any censoring, the primary efficacy endpoint will be analyzed using Log-rank test and Gehans Wilcoxon test, and the result will be presented by p-values from the two tests. Also the table will present count of censoring reasons and 25th percentile, median, 75th percentile of time from administration of study drug to resolution. Kaplan-Meier plots will be presented.

CONFIDENTIAL

Statistical Analysis Plan

If there are no censoring data, sensitivity analysis using tipping point analysis under Missing Not at Random (MNAR) will be also performed to explain varying cases about average unobserved outcomes dropouts on two treatment groups.

Sensitivity Analyses which alter resolution conditions of primary efficacy analysis will be performed on the ITTI population. Following two endpoints will be assessed as described for the primary efficacy endpoint.

- Time (in days) to resolution of influenza symptom (respiratory and constitutional symptoms)

In the analysis, fever is not considered and the definition of resolution of symptom is the same as those of primary efficacy analysis.

- Time (in days) to resolution of influenza symptom and fever

In the analysis, threshold of resolution of fever is changed to 37.8°C and the definition of resolution of symptom is the same as those of primary efficacy analysis.

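### The trial is meant to obtain an effect size versus placebo, but the primary analysis pre-specifies no between-group estimate with a confidence interval for either dose

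*SAP*

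**What the plan says.** **Purpose.** Protocol 2.2 says "This study was designed to obtain an effect size of CT-P27 in comparison to placebo". SAP 5.2 (and Protocol 8.1 likewise) says "This study is designed to obtain effect sizes of 2 different CT-P27 treatment groups and placebo group". SAP 1.1 gives the use: "Information on effect size, as well as the safety and PK will be used in the selection of doses for subsequent clinical studies". The sample-size text treats effect size as a reduction in days paired with an SD: 1.8 days with SD 3, and alternatively 1.5 days with SD 2.9.

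**Primary result.** SAP 10.1 compares each dose with placebo.
- With no censoring it uses the Wilcoxon rank-sum test: "The results of the analysis will be summarized using p-values". Protocol 8.5.1 agrees: the difference "between placebo and CT-P27 based on Wilcoxon rank-sum test will be presented by p-values".
- With any censoring the SAP uses log-rank and Gehan tests, and "the result will be presented by p-values from the two tests". It adds counts of censoring reasons, the three quartiles of time to resolution and Kaplan-Meier plots.

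**General rule.** SAP 5.1 says data are "described using descriptive statistics (including number [n], mean, median, Standard Deviation (SD), minimum, and maximum) for continuous variables".

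**Confidence intervals.** The only one named in either document is for the slope of the PK dose-proportionality model (Protocol 8.5.3, SAP 11.1.2). SAP 13 and the primary table titles in SAP 14.7 add no efficacy contrast or interval.

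**The concern.** The plan sets out to estimate, then reports a test. A p-value gives neither the size of a dose's effect nor how precisely it is known, and the next design decision needs both. The two sensitivity analyses that change the resolution definition are to be assessed in the same way as the primary endpoint, so they too would be compared through p-values.

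The arm-level summaries do not close the gap. A reader can subtract medians or, with no censoring, means. But SAP 10.1 does not say which contrast is the trial's effect size or attach an interval to it. It also does not say what replaces a difference in means once times are censored. If that is settled after unblinding, the result can influence the choice.

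**Working it through.** **Inputs (SAP 5.2, Protocol 8.1).** 63 evaluable per CT-P27 arm and 38 on placebo; difference 1.8 days; SD 3 days; two-sided 5%; rank-sum test; stated power 80%.

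**1. The plan's own figure.**
- SE of a difference in means = 3 × √(1/63 + 1/38) = 0.616 days.
- The rank-sum test has efficiency 3/π = 0.955 under normality, so the equivalent SE is 0.616/√0.955 = 0.631.
- Power = Φ(1.8/0.631 − 1.96) = Φ(0.89) = 81%. A 20,000-run simulation of the test under a normal shift gave 79.9%.
- 63 + 63 + 38 = 164, and 164/0.9 = 182.2, rounded up to 183.

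The stated 80%, 164 and 183 all reproduce. No figure in the plan is disputed.

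**2. The precision that p-values leave out.**
- Difference in means: half-width = 1.96 × 0.616 = 1.21 days, or 1.21/1.8 = 67% of the design effect. An observed 1.8 gives 1.8 ± 1.21 = 0.59 to 3.01 days.
- Hodges-Lehmann shift (matched to the rank-sum test): half-width = 1.96 × 0.631 = 1.24 days. An observed 1.8 gives 0.56 to 3.04.
- Other arm sizes (mean difference): 1.14 days with 70 versus 43, and 1.27 days with 57 versus 34.
- A result reported only as p = 0.04 would correspond to a shift of 2.054 × 0.631 = 1.30 days, with an interval of about 0.06 to 2.53.

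**3. Does the choice of summary matter? Illustration only.** Trials of 63 versus 38 were simulated with full follow-up and a true mean reduction of 1.8 days. Within each trial, the differences in means and medians and the Hodges-Lehmann shift were compared.

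| Assumed times to resolution | Average range of the three | 90th percentile |
|---|---|---|
| Gamma, SD 3, placebo mean 4.5–5.5 days | 0.5–0.6 days | about 0.9–1.0 days |
| Normal, SD 3, means 5.0 and 3.2 days | about 0.4 days | about 0.75 days |

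The distributions are assumptions; the documents give none. The Hodges-Lehmann shift is not a planned output.

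**4. Effect of a restricted-mean horizon.** Under the same gamma assumption, a true 1.8-day mean reduction appears as about 1.3–1.5 days at a 6-day horizon, 1.7–1.8 at 10 days and 1.8 at 13 days.

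**The case against.** **Estimates are planned.** A reader might infer that the plan gives no estimate at all. It does not go that far: quartiles and Kaplan-Meier plots are specified for the censored case, and SAP 5.1 supplies n, mean, median and SD generally. With no censoring, n, mean and SD are enough to compute a difference and its interval. This stands, and it limits the point to the between-group estimate and its precision.

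**The documents indicate what they mean by effect size.** The sample-size text gives a reduction in days with an SD, which points to a mean-difference scale. This also stands. What is missing is narrower: SAP 10.1 does not carry that quantity into the analysis, give it an interval or adapt it to censoring.

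**The width is sampling error.** The 1.2-day half-width follows from the sample size and would be the same under any reporting rule. True; it shows why the interval must be reported and does not measure harm from the omission.

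**Leaving the summary open has a known cost.** A reader might infer from step 3 that the omission will mis-size the next trial by a definite amount. The documents do not support that. The spread depends on an assumed distribution and on full follow-up, and medians or Hodges-Lehmann shifts cannot simply be put into a sample-size formula for means.

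**This is phase IIb proof of concept.** That does not weaken the point, because estimation is the purpose the documents give for this trial.

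**Conclusion.** The point holds. For each dose against placebo, the only between-group primary result specified is a p-value, with or without censoring. The plan as written therefore does not deliver its stated quantity with its precision. Under the plan's inputs that precision is about ±1.2 days around a 1.8-day design effect, assuming SD 3, 63 versus 38 evaluable and no censoring.

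Confidence is high for the omission, which rests on the text alone. The spread between summaries is illustrative. Nothing here suggests that the tests are invalid or that the sample size is wrong. It should be corrected before unblinding, but it does not undermine the trial.

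**What to change.** In SAP 10.1, for each dose versus placebo, pre-specify before unblinding **one main between-group difference in days with a 95% confidence interval**, usable with or without censoring.

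- **Example:** the Kaplan-Meier difference in restricted mean time to resolution. With no censoring and a long enough horizon it equals the difference in means, the scale of the sample-size text.
- **Horizon:** fix one at the blinded data review meeting. The regular diary covers Day 1 to Day 8, but SAP 10.1 says diary data including records taken as "a part of suspicious ADE assessment will be used for the analysis". Entry to that extra follow-up depends partly on investigator opinion (Protocol 6.2.5), so support beyond Day 8 should be checked on blinded pooled data. The first report takes second-season data only to Day 15 (SAP 1.1).
- **Support:** the Hodges-Lehmann shift with 95% interval when the rank-sum test applies; a hazard ratio with 95% interval when the log-rank test applies.
- **Consistency:** report the same estimate in the sensitivity analyses and add it to the primary tables in SAP 14.7.

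Another measure would also close the gap if it is named in advance with its interval and handles censoring.

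**Cost:** SAP wording and a little programming; no new data or subjects. The interval may not agree exactly with the test p-value. A restricted-mean difference shrinks at a short horizon, so it should not then be read against the 1.8-day target.

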10.2 Secondary Efficacy Analyses

The secondary efficacy endpoints will be analyzed on the ITTI and ITT populations. For time-to-event analyses of secondary efficacy endpoints, records on diary for suspicious ADE assessment and unscheduled assessment of site body temperature will be used together with data from regular scheduled assessment.

- The following secondary efficacy endpoints will be analyzed using a Kaplan Meier model to assess differences between placebo and CT-P27. Missing time of completion of diary will be considered as described in the section for the primary efficacy endpoint:

- Time (in days) to resumption of normal activity as reported in Domain 2 of the Flu-iiQ™: [Start date/time of resumption of normal activity] – [Start date/time of study drug administration]

The resumption of normal activity has occurred if the degree of difficulty of all of the Domain 2 items are of no difficulty or some difficulty for at least 24 hours.

- Time (in days) to return to normal body temperature (<37.0°C) for at least 24 hours : [Start date/time of resolution of fever] – [Start date/time of study drug administration]

Data of body temperature recorded on the diary as well as the ones measured from the sites will be used to determine the return time to normal body temperature for at least 24 hours.

However, assessments which exceeds 24 hours measurement interval will be excluded because of lack of consecutiveness in determining the resolution.

If time of measurement of body temperature from site is missing, then the time will be imputed based on time of study drug administration such that missing body temperature assessment time on Day 3 will be imputed as: Infusion time + 48 hours. Missing times on other days will be imputed in the same manner.

- Time to resolution of individual symptoms for at least 24 hours as reported in Domain 1 of the Flu-iiQ™: [Start date/time of resolution of individual influenza symptoms] – [Start date/time of study drug administration]

The resolution of individual influenza symptoms will be determined as described for the primary efficacy endpoint.

- Severity of symptoms as recorded on the Domain 1 of the Flu-iiQ™
 - Impact of influenza symptoms consist of 4 scales of the items in Domain 1 (respiratory symptoms, constitutional symptoms, systemic symptoms, total symptoms)
 - Respiratory symptoms: cough, sore throat, and nasal congestion

Statistical Analysis Plan

- Constitutional symptoms: headache, feeling feverish, body aches and pains, and fatigue
- Systemic symptoms: headache, feeling feverish, body aches and pains, fatigue, neck pain, interrupted sleep, and loss of appetite
- Total score: all items in Domain 1

Descriptive statistics of actual value and change from baseline for average score in each scale will be presented by treatment group at each visit.

If there are missing values in items in Domain 1, missing data will be handled according to section 10.3.

- Descriptive analysis for AUC of average symptom score from date of baseline assessment to last measurable value of subjects who have at least one post-baseline result.

If there are missing values in average symptom scores between observed ones, the missing values are assumed to fall linearly between observed values.

- Mean daily symptom score on the Domain 1 of the Flu-iiQ™

Average of total symptom score for each time point will be plotted with the SD of mean score.

- Incidence of symptoms on the Domain 1 with Grade 2 or Higher

The proportion of subjects who developed any of the 7 individual influenza symptoms (cough, sore throat, nasal congestion, headache, feeling feverish, body aches and pains, and fatigue from Flu-iiQ™ Domain 1) with moderately or severe in intensity (Grade 2 or higher) will be calculated from baseline to Day 8. Most severe score will be counted per each day. Subjects with incomplete data and no recorded symptoms will not be counted (i.e. did not experience symptoms Grade 2 or higher).

All item scores of Flu-iiQ™ will be listed by each domain and time point. Additional listing for Flu-iiQ™ will be provided including average score of Domain 1 (respiratory, constitutional, systemic, total symptom score), Domain 3, Domain 4 and AUC of Domain 1.

- Viral shedding in nasopharyngeal swab samples

Viral shedding (titers) of swab samples based on qPCR and cell culture will be evaluated at the scheduled collection times. The listing will include titer results, whether the influenza A is confirmed and Area under the Curve (AUC) of viral loads. However, since cell culture results have information of both influenza A and B, the listing and tables for cell culture will present analysis results regardless of influenza type. Changes in viral shedding will be assessed as the change from baseline in \log_{10} vp/mL and \log_{10} TCID₅₀/mL for qPCR and cell culture respectively. If viral loads are lower than LLoQ (2.18 for qPCR), they will be treated as value without inequality sign. Whereas viral load lower than LLoQ for cell culture (0.75) will be considered as negative value and a negative value will be treated as 0. If the subtype of influenza A is "H1", "NA" or "Unknown", the virus titer from HA assay will be used for cell culture analysis. Otherwise, if the subtype is "H3", the virus titer from NP ELISA will be used.

These will be summarized for each treatment group and collection time.

The following analyses will also be performed:

- Summary of viral shedding results; percentage of subjects with positive/negative viral shedding at each visit (baseline, day 2, 3, 5, 8)
- Duration (in days) of viral shedding; from date/time of baseline assessment to last positive sample. Subjects with at least one positive sample after baseline will be included in the summary.

Statistical Analysis Plan

- AUC of viral levels; from date of baseline assessment to last measurable value of subjects who have at least one post-baseline result (including BLQ (Below the Limit of Quantification) and negative values). If there are BLQ or missing values between measurable values, they are assumed to fall linearly between measurable values.
- Change from baseline in descriptive statistics of viral shedding of Swab Samples; descriptive statistics of actual value and change from baseline for viral shedding of swab samples will be presented by treatment group at each visit.
- Mean viral load titer (log values)
Mean viral load titer for each scheduled time point will be plotted with the SD of mean value.

- Incidence of secondary complications of influenza

The presence of secondary complications of influenza A infection will be determined by the Investigator's assessment of the subject's clinical condition. An Adverse Event (AE) will be considered as secondary complication if "Yes" is checked for the question, 'Is this Adverse event Secondary Complications of Influenza?' of the 'Adverse Event' page of eCRF.

The number and percentage of subjects with secondary complications of influenza will be summarized by treatment group and PT. Secondary complications of Influenza will be summarized by SOC and PT, displaying the number and percentage of subjects with at least one secondary complications of Influenza. Secondary complications of influenza A will be listed including following variables: SOC, PT and reported term; Start date/time; End date/time; Duration of AE in days; Frequency; Outcome; Intensity; Relationship to study drug.

The number and percentage of subjects with secondary complications of influenza who had used or never used antibiotics/antifungal/antiviral will be summarized by treatment group and overall for each PT of secondary complication AE. The summary of secondary complication AE will be presented in alphabetical order of PTs. The antibiotics/antifungal/antiviral for subjects with secondary complications will be discussed at the blind DRM. Algorithms for capture rule of the antibiotics/antifungal/antiviral is presented in [Appendix 14.4.1](#) and ATC code list is presented in [Appendix 14.4.2](#).

- QoL measures as reported in Domain 3 and Domain 4 of the Flu-iiQ™ (effect on feelings, concerns due to influenza)

Each item will be scored with a 4-point scale (0: Not at all, 1: Somewhat, 2: Moderately, 3: Extremely), and the QoL will be presented as the average score of each domain, and will be summarized with descriptive statistics by collection time and treatment group.

- Physician Assessment

Physician assessment including ears, nose, throat, sinuses, lungs, potential complications of Influenza will be performed at each scheduled time (Screening, Day 2, Day 3, Day 5, Day 8, Day 110/EOS). The results will be classified as "Normal", "Abnormal, NCS", "Abnormal, CS" or "Not done" with specification. The number and percentage of subjects regarding the result of physician assessment will be summarized by treatment group and system in the form of a shift table to detect changes from baseline in the ITT population. All physician assessment data will be listed for each subject by treatment group, visit, system and interpretation in the ITT population.

